5.3.1 Additional Secondary Outcomes

Analysis of near control, angle magnitude, stereoacuity, and treatment compliance will be performed as described below.

5.3.1.1 **Deterioration**

At both the 12-month and 18-month time points, the cumulative proportion of subjects who meet either of the deterioration criteria (*section 3.7*) by the time point will be estimated for each treatment group using the proportional hazards model to enable adjustment for potential residual confounding. The adjusted cumulative probability estimate will then be compared between treatment groups using the Z-test. The cumulative proportion of patients who meet stereoacuity deterioration criteria by the time point and the cumulative proportion of patients who have constant exotropia by the time point will also be estimated and compared between treatment groups using similar methods. Analytic methods which account for possible informative censoring will be explored for handling subjects who start non-randomized treatment for IXT. Such methods will also be explored for the stereoacuity deterioration and motor deterioration outcomes.

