3.1 Primary Analysis: Motor or Stereo Deterioration

Participants who meet either of the following at any visit will be considered to have met deterioration criteria.

- Motor deterioration: Control of the exodeviation measures 5 (constant exotropia) on all three assessments at distance and near. The exodeviation does not need to be constant throughout the entire exam provided that it is constant during all three assessments of control. (The study requires that a participant cannot be enrolled if the control of the exodeviation at near measures 5 on all three assessments at baseline; hence all participants in the study are eligible for motor deterioration.)
- Stereoacuity deterioration: Drop in near stereoacuity of at least 2 octaves (at least 0.6 log arcsec) from enrollment stereoacuity, or to nil, confirmed by a retest. (Participants with nil stereoacuity at enrollment will not be able to deteriorate with respect to a drop in near stereoacuity but are included in the analysis as they may have motor deterioration.)

299 Hazard of deterioration from a proportional hazards model will be compared by treatment
300 group using the hazard ratio, and cumulative proportions deteriorating in each treatment
301 group at 12 and 18 months will be reported. The cumulative proportion estimates from
302 the proportional hazard model will be compared between treatment groups using a Z-test
303 for proportions if at least one of the proportions is between 0.05 and 0.95. If both
304 proportions are not between these two numbers, they will not be compared statistically.
305 The proportional hazards model will adjust for baseline level of the components of the
306 outcome, i.e. distance control, near control, and near stereoacuity. The population mean
307 of the covariates in the proportional hazards model will be used for cumulative
308 probability estimation. We will only adjust for these baseline-level components of the
309 outcome because deterioration rates were low in IXT2,¹ making adjustment for more than
310 a few covariates potentially problematic. The observed data will be used in these
311 analyses.

312
313 Any observation with a missing value for any of the baseline factors will be excluded
314 from the analysis. However, the number of missing values is expected to be low given
315 that the testing of these baseline factors is required at enrollment by protocol. If either

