316 motor or stereo outcome data are missing at a follow-up visit and these data are available
317 at a later visit, the deterioration status will be carried forward from the visit previous to
318 the missing visit. The participants who are lost to follow up without meeting deterioration
319 criteria will be considered censored as of the last completed follow-up visit.

320
321 The participants who start non-study treatment (i.e., treatment other than overminus or
322 non-overminus) for IXT will be censored 0.1 month after the visit when the non-study
323 treatment was prescribed. Participants who are treatment crossovers (non-overminus
324 group participants who are prescribed overminus; overminus group participants who have
325 overminus spectacles formally discontinued against protocol) will have observed
326 deterioration status data included in analysis, i.e., will not be censored on the basis of
327 starting a non-randomized treatment (i.e., any treatment other than the one assigned by
328 the study at randomization). The proportional hazards model time variable will be
329 discrete with times corresponding to the follow-up time of study visits.

330
331 The proportional hazards assumption will be checked by testing for a time by treatment
332 interaction in the model, as well as by visual inspection of Kaplan-Meier time-to-event
333 curves. In the event the proportional hazards assumption is not met, an alternative
334 analysis such as a weighted, stratified comparison of Kaplan-Meier estimates will be
335 considered.

336
337
338

339 **3.2 Secondary Analysis: Cause-Specific Deterioration**

340 If the overall deterioration treatment group comparison (Section 3.1) is performed and is
341 significant, then the cumulative incidence of cause-specific deterioration (stereo ONLY
342 and motor ONLY) by 12-months and 18-months will be estimated and compared between
343 the treatment groups using the cumulative incidence function to account for the
344 competing risks of starting treatment due to deterioration from a cause other than the

345 cause of interest, or starting treatment against protocol. To control for multiplicity, alpha
346 will be split between the two time points (12 and 18 months), and a gatekeeping strategy
347 will be used within each time point, i.e., the 18-month difference will be tested only if the
348 12-month difference is statistically significant. These analyses are considered post-hoc, as

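### SAP 3.1 reports cumulative deterioration for one child with mean covariates, not for the randomised groups; at low event rates this understates the risks and their difference if the covariates are prognostic.

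*SAP*

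**What the plan says.** SAP 3.1 (Motor or Stereo Deterioration) sets out the analysis as follows.

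- **Model.** "Hazard of deterioration from a proportional hazards model will be compared by treatment" group, using the hazard ratio. The time variable is "discrete with times corresponding to the follow-up time of study visits".
- **Covariates.** The model adjusts for the baseline level of the components of the "outcome, i.e. distance control, near control, and near stereoacuity. The population mean" of these covariates is then where the risks are evaluated: it "of the covariates in the proportional hazards model will be used for cumulative" probability estimation.
- **Reported risks.** Cumulative proportions deteriorating in each treatment "group at 12 and 18 months will be reported. The cumulative proportion estimates from" the model go into the test.
- **Test and threshold.** The arms are compared by a Z-test "for proportions if at least one of the proportions is between 0.05 and 0.95. If both" lie outside that range, no statistical comparison is made.
- **Expected rates.** Adjustment is confined to baseline components of the "outcome because deterioration rates were low in IXT2,¹ making adjustment for more than" a few covariates potentially difficult. No figure is given.

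SAP 3.2 runs the cause-specific analysis only if the 3.1 comparison has been performed and is significant.

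Protocol 5.3.1.1 asks for the cumulative proportion of subjects in each group who meet either criterion, estimated with a proportional hazards model to allow adjustment. It continues: "The adjusted cumulative probability estimate will then be compared between treatment groups using the Z-test". It does not say at what covariate values the adjusted probability is to be taken. Neither document averages predictions over participants.

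**The concern.** A proportion deteriorating in a treatment group is an average over the children in that group. The model's risk at the mean covariates is the risk of a single hypothetical child. Risk is a curved function of the linear predictor, so the two coincide only if the covariates carry no prognostic information. Here the covariates are baseline levels of the outcome's own components, so some prognostic spread is plausible.

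Two things are at stake. The published group proportions and their difference may not describe the trial population. The model-based proportions also decide whether a test is done at all: if both estimates fall below 0.05, the Z-test is skipped, and with it the Section 3.2 analysis.

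**Working it through.** **Inputs from the documents.** The prediction rule, the three covariates, the 0.05 to 0.95 rule and the expectation of low rates are from SAP 3.1. The total of 384 children randomised 1:1 is from Protocol 1.16. Neither document gives a deterioration rate, hazard ratio or power for this outcome, so there is no stated figure to reproduce.

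**Assumptions.** Hazard ratio 0.5. The linear predictor is normal with standard deviation *s*, shown from 0.2 to 1.0. A child 1 SD above the mean then has exp(2*s*) times the hazard of a child 1 SD below: 1.5, 1.8, 2.7, 4.5 and 7.4 for *s* = 0.2, 0.3, 0.5, 0.75 and 1.0.

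**Formulas.** Let *p* be the risk at the mean covariates and H = -ln(1 - *p*).

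- Average risk = E[1 - exp(-H·exp(*s*Z))], with Z standard normal.
- For the overminus arm, replace H by 0.5·H.
- At low risk the average is roughly *p*·exp(*s*²/2). For *s* = 0.5 that is 5.0% × 1.133 = 5.7%, against 5.6% exactly.

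**Direction.** With u = H·exp(linear predictor), the second derivative of the risk is u(1 - u)·exp(-u). It is positive while u < 1, that is, while risk is below 1 - exp(-1) = 63%, so there the risk at the mean lies below the mean risk. For the difference between arms, the same expression must be larger in the higher-risk arm. It rises with u until u² - 3u + 1 = 0, at u = 0.382, a risk of 32%. For small *s*, therefore, the difference is understated when both arms are below about 32%.

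**Size.** The control risk at the mean is 5.0% in the second column. In the third it is 6.0%, so the overminus risk at the mean is 1 - 0.94^0.5 = 3.05% and the difference at the mean is 2.95 points.

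| *s* (assumed) | Average risk when risk at mean is 5.0% | Average difference when difference at mean is 2.95 points |
|---|---|---|
| 0 | 5.0% | 2.95 |
| 0.2 | 5.1% | 3.00 |
| 0.3 | 5.2% | 3.07 |
| 0.5 | 5.6% | 3.28 |
| 0.75 | 6.4% | 3.70 |
| 1.0 | 7.6% | 4.26 |

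Read the other way, a true average control risk of 5% would be reported as 4.6%, 4.0% or 3.2% for *s* = 0.4, 0.7 or 1.0.

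**Simulated Cox fits** (384 children, visits at 6, 12, 15 and 18 months, hazard ratio 0.5, 300 runs per setting). At a true control risk of 6% and *s* = 0.7:

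| Estimate | Control / overminus | Difference (points) |
|---|---|---|
| At mean covariates | 4.5% / 2.4% | 2.1 |
| Averaged over children | 5.9% / 3.2% | 2.7 |
| Crude proportion | 6.0% / 3.3% | 2.8 |

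Both model-based estimates sit slightly below the crude one because of tied visit times, which is a separate matter.

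**The 0.05 rule in the same simulations.** Share of runs in which at least one proportion reached the range that permits a test:

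| True control risk | *s* | At mean | Averaged |
|---|---|---|---|
| 6% | 0.4 | 54% | 69% |
| 6% | 0.7 | 34% | 69% |
| 10% | 0.7 | 93% | 100% |
| 20% | 0.7 | 100% | 100% |

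The threshold matters only when the true risk is close to 5%.

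**The case against.** The strongest reply is that this is a disclosed choice of estimand with a small effect. The protocol asks for an adjusted probability, the SAP says how it is evaluated, and a reference profile is transparent and reproducible. The documents do not show that the covariates are strongly prognostic, and the design may limit their spread. Protocol 2.2 requires a mean distance control of at least 2 and excludes a near score of 5 on all three assessments. Under Protocol 3.4, Table 2, a child starting at 400 or 800 arcsec can lose stereoacuity only to nil, and a child already at nil cannot deteriorate on stereo. At *s* = 0.2 the shift is about 2% relative. This stands as a limit on size. It does not change what is being estimated, because both documents describe the result as the proportion deteriorating in each group.

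A reader might infer that the Z-test is invalid or loses power in proportion to the smaller difference. The documents and calculations do not support that. With a treatment hazard ratio of 1, the at-mean risks are equal in both arms and so are the averaged risks, so the null hypothesis is the same. Simulation with 384 children, a control risk of about 11% or lower and 600 runs per setting compared the two tests:

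| *s* | Rejection with no effect, at mean vs averaged | Power at hazard ratio 0.5, at mean vs averaged |
|---|---|---|
| 0.4 | 5.0% vs 5.0% | 47% vs 48% |
| 0.7 | 5.0% vs 5.3% | 44% vs 46% |
| 1.0 | 5.7% vs 6.3% | 44% vs 48% |

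The estimate and its standard error shrink together. The hazard ratio, which is also reported, does not depend on the prediction rule.

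A reader might also infer that a mean child is meaningless because stereoacuity can be nil. The SAP expresses its stereoacuity criterion in log arcsec, and control is a mean of three scores. No numerical harm follows from this point alone.

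**Conclusion.** The point holds in conditional form. SAP 3.1 estimates the risk of one profile where it and the protocol name a group proportion. At the low rates the SAP expects, and if the covariates are prognostic, the reported risks and their difference are too low. The shift is about 2% relative at an SD of 0.2. At an SD of 1.0, 5.0% corresponds to 7.6% and 2.95 points to 4.26. The SDs and the hazard ratio of 0.5 are assumptions, and the documents do not say which row of the table applies.

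An unconditional claim of understatement would go too far. There is no bias if the covariates are not prognostic, and the direction can reverse at high risk: at a true control risk of 50% the difference is overstated by 1% to 30% for *s* from 0.2 to 1.3.

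The practical consequence beyond calibration is the 0.05 rule. With a true risk near 5%, the choice of prediction can decide whether the Z-test and the Section 3.2 analysis are run. Deterioration is a secondary outcome under Protocol 5.3.1, and the primary analysis of distance control is not touched. This is a worthwhile low-cost improvement, not a serious flaw.

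**What to change.** Keep the model and covariates. From the same fit, predict every analysed child's 12- and 18-month risk twice, once under each arm, and average each set over all analysed children. Report the two standardised risks and their difference with a bootstrap or delta-method standard error. Apply the 0.05 to 0.95 rule and the Z-test to these values, and leave the hazard ratio as planned.

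The cost is slightly more coding and a resampling or delta-method standard error. If the data have already been analysed, give the standardised result alongside the planned estimate and label it as an addition.

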					
Section 2.1.7: Added sensitivity analysis #5 that will include additional adjustment factors.
 
Section 2.1.9: Addressed how imputation will be handled under Protocol Amendment II for participants who missed certain visits.
 
Section 2.2: Explained that analysis will be repeated in a cohort limited to those who were prescribed weaning before Protocol Amendment II.
 
Section 2.3: Revised to say that effect of weaning will only be calculated in the overminus group and will not use ANCOVA but rather a t-test or Wilcoxon depending on normality of distribution. Also edited to say that the analysis will be limited to those who were prescribed weaning, and deleted part about Bonferroni correction as it will not be done here. Also added paragraph on calculation of the retention of 12-month treatment effect at 18 months.
 
Section 3.1: Edited to say that treatment groups will be compared using a Z-test as long as one of the proportions is between 0.05 and 0.95. Edited adjustment factors, deleting distance PACT and leaving only baseline factors of the deterioration clinical outcomes (stereo and control). Added paragraph on how proportional hazards assumption will be checked.
 
Section 3.2: Edited to say that cause-specific deterioration will be calculated only if overall deterioration is significant. Revised adjustment factors as in Section 3.1. Explained that alpha will be split between time points and gatekeeping strategy will be used. Stated that participants with nil stereo at baseline will be excluded.
 
Deleted sensitivity analysis on deterioration outcome (originally Section 4.3).
 
Section 4: Stated what statistics will be tabulated/calculated for all outcomes.

--	--	--	--	--	---

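### SAP 3.2 estimates cause-specific deterioration only after a significant composite result, so the by-arm estimate of motor deterioration specified in Protocol 5.3.1.1 may go unreported

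*SAP*

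**What the plan says.** Protocol 5.3.1.1 plans the composite of motor or stereoacuity deterioration at 12 and 18 months. It then adds the two components: after stereoacuity deterioration it says that the "cumulative proportion of patients who have constant exotropia by the time point will also be estimated and compared between treatment groups using similar methods". No condition is attached.

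SAP 3.1 defines motor deterioration as a control score of 5 on all three assessments at both distance and near, at any visit. It reports composite cumulative proportions by arm at 12 and 18 months. The Z-test on those proportions is run "for proportions if at least one of the proportions is between 0.05 and 0.95. If both" arms fall outside that range, there is no statistical comparison. The same section limits its covariates to the components of the "outcome because deterioration rates were low in IXT2".

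SAP 3.2 then opens: "If the overall deterioration treatment group comparison (Section 3.1) is performed and is" "significant, then the cumulative incidence of cause-specific deterioration (stereo ONLY" "and motor ONLY) by 12-months and 18-months will be estimated and compared between" the arms. Estimation and comparison therefore sit behind the same condition. The revision history for SAP version 2.0 shows that this was intended: "Edited to say that cause-specific deterioration will be calculated only if overall deterioration is significant".

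Later in SAP 3.2, an additional analysis counts only stereoacuity deterioration and excludes children with nil stereoacuity at baseline. Its own sentence carries no condition, although its place within 3.2 leaves some ambiguity.

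**The concern.** A condition on the p-value can be defended as control of multiplicity. A condition on the estimate is harder to defend, because a descriptive estimate with its interval makes no claim of significance. Here the condition covers both, and so narrows an outcome that the protocol set out to estimate by arm.

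There are two hurdles: the composite comparison must be performed and it must be significant. If deterioration is uncommon, both are hard to clear. The trial could then end without a by-arm cumulative estimate of how many children reached constant exotropia at distance and near. The primary analysis of distance control is not affected.

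**Working it through.** **Which results depend on the condition**

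| Result by arm | Protocol 5.3.1.1 | SAP 3.1 and 3.2 |
|---|---|---|
| Composite proportion, 12 and 18 months | planned | reported without condition; Z-test subject to the 0.05 to 0.95 rule |
| Stereoacuity deterioration | estimated and compared | cause-specific estimate conditional; additional stereo-alone analysis reads as unconditional |
| Motor deterioration (constant exotropia) | estimated and compared | conditional only |

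**Inputs**
- Children per arm: 163 (326/2, the evaluable number in Protocol 5.7.1) to 192 (384/2, Protocol 5.7.2). The midpoint is about 177 (355/2, from the 355 expected 18-month visits in SAP 4.2.2).
- Test: two-sided 5%, assumed for the composite.
- Hurdle 1: at least one observed proportion between 0.05 and 0.95 (SAP 3.1).
- Deterioration rates: assumed, because the documents give none.

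**The plan's own figure.** No power is stated for deterioration, so only the arm size can be reproduced. 2 × (1.96 + 1.2816)² × 1.8² / 0.65² = 161.2, or 162 per arm. The t-based solution is 162.1, hence 163 per arm and the stated 326. Then 163/0.85 = 191.8, which gives 192 per arm and the stated 384.

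**Formula.** With observed proportions a and b, n per arm and m = (a + b)/2, the condition is met when hurdle 1 holds and |a − b| / √(2m(1 − m)/n) > 1.96. I summed the binomial probabilities of all pairs of counts that satisfy both. Hurdle 1 needs at least 9 events in one arm at n = 163 (0.05 × 163 = 8.15) and at n = 177 (8.85), and 10 at n = 192 (9.6).

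**One case by hand, 8% v 4%, n = 177.** m = 0.06. Null SE = √(2 × 0.06 × 0.94/177) = 0.02524. Alternative SE = √((0.08 × 0.92 + 0.04 × 0.96)/177) = 0.02515. Power ≈ Φ((0.04 − 1.96 × 0.02524)/0.02515) = Φ(−0.377) = 0.353. Exact summation gives 0.350.

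| Assumed composite | Test performed (n = 163 / 177 / 192) | Condition met (n = 163 / 177 / 192) |
|---|---|---|
| 2% v 1% | 1% / 1% / 1% | 1% / 1% / 1% |
| 4% v 2% | 21% / 29% / 25% | 11% / 14% / 13% |
| 5% v 2.5% | 44% / 54% / 51% | 18% / 21% / 22% |
| 6% v 3% | 67% / 76% / 74% | 24% / 27% / 28% |
| 8% v 4% | 93% / 96% / 96% | 32% / 35% / 38% |
| 20% v 10% | 100% / 100% / 100% | 72% / 76% / 79% |
| 15% v 5% | 100% / 100% / 100% | 88% / 90% / 92% |

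**Cancelling effects.** Assume motor 6% v 2% and stereo 2% v 6%, with no child meeting both criteria, so that the composite is 8% v 8%. At n = 177 the condition is met in about 5% of trials. The motor difference taken alone would be nominally significant in about 50%.

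**Limits of the calculation.** It uses raw proportions in place of model-adjusted ones and a single time point. SAP 3.2 does not say which Section 3.1 result must be significant. If the hazard-ratio comparison were meant, hurdle 1 would not apply. The same Z-test without hurdle 1 gives 10-11% at 2% v 1%, 17-20% at 4% v 2% and 21-25% at 5% v 2.5%; from 8% v 4% upward the figures hardly change.

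**The case against.** **The change is authorised and disclosed.** The opening of Protocol Chapter 5 says the SAP supersedes it, Protocol 5.3 defers details to the SAP, and the revision history records the condition. SAP 3.2 also calls the analyses post hoc, because version 1.0 of the protocol and SAP lacked them. This stands as far as it goes. But the SAP is based on Protocol 3.0, which does list the component comparisons. The post-hoc label supports caution over p-values and does not explain withholding estimates.

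**A reader might infer that both components are lost and that opposite effects would stay hidden.** The documents do not support that. With the composite and stereo-alone results both reported, an opposite motor effect could be partly inferred. It could not be recovered exactly, because the stereo-alone analysis drops children with nil baseline stereoacuity and a child may meet both criteria.

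**A reader might infer that motor deterioration by arm will probably never be shown.** That depends on rates the documents do not give, and fails for large effects such as 20% v 10%. Part of the SAP, from within Section 4.3.1 to Section 5.2.1, was also not available here, so nothing can be said about its content.

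**Other outputs touch on constant exotropia.** Protocol 4.4 has new cases reported, Protocol 5.5 tabulates reasons for non-randomized treatment by arm, and SAP Section 4 tabulates distance and near control by arm at 12 and 18 months. These help, but none is a cumulative by-arm estimate of a score of 5 on all three tests at both distances at any visit. Constant exotropia at distance is already allowed at entry, so the distance scores alone cannot supply it.

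**Two further readings lack support.** No text ranks motor deterioration as the more severe component, and none says that the two components reflect different mechanisms.

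**Intervals can be read as tests.** This is fair, and is the reason for the descriptive label in the fix.

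**Conclusion.** The point holds in a limited form. SAP 3.2 places estimation as well as testing of the cause-specific components behind a composite comparison that must be both performed and significant, and Protocol 5.3.1.1 has no such condition. The by-arm estimate at risk is motor deterioration.

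How often it would be withheld depends on assumed rates. For composites from 2% v 1% to 8% v 4%, the condition is met in about 1% to 38% of trials. With cancelling component effects it is met in about 5%, and at 20% v 10% in 72-79%. The consequence is therefore likely if deterioration is uncommon or the effects offset each other, and unlikely if the effect is large. The only guide in the documents is that rates were low in the earlier study. This concerns completeness of reporting for a secondary outcome and does not bear on the validity of the primary result.

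**What to change.** Replace the conditional sentence in SAP 3.2 with text such as:

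> The cumulative incidence of motor deterioration and of stereoacuity deterioration at 12 and 18 months will be reported for each treatment group, with the between-group difference and 95% confidence interval, regardless of the result in Section 3.1. These estimates are descriptive. P-values will be given only if the Section 3.1 comparison is significant.

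The SAP should also name the Section 3.1 result that releases the p-values. If the sponsor prefers to keep the condition on estimation, the SAP should give its reason for departing from Protocol 5.3.1.1.

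The convention is already in the SAP: Section 4.2.1 shows subgroup differences with 95% intervals and no p-values, and Section 5.4 does the same for the extension outcomes.

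The cost is one extra table with no new data collection. Events will be few. At an assumed motor rate of 4% v 1% and 177 per arm, about 7 and 2 children are affected (0.04 × 177 = 7.1; 0.01 × 177 = 1.8). The interval on the 3-point difference has a half-width of 1.96 × √((0.04 × 0.96 + 0.01 × 0.99)/177) = 0.032, or about 3.2 points. Some readers may treat such intervals as tests, which the descriptive label reduces but does not remove.
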